11.0 Vulnerable Populations*

11.1 If the research involves individuals who are vulnerable to coercion or undue influence, describe additional safeguards included to protect their rights and welfare.

N/A

12.0 Local Number of Subjects

12.1 Indicate the total number of subjects to be accrued locally.

- For Aim 1, ten (10) experts will be selected to review and rate the components developed for the B-SWELL intervention.
- For Aim 2, a total of fifty (50) midlife Black women will be recruited for participation in the pilot of the intervention.
 - 12.2 If applicable, distinguish between the number of subjects who are expected to be enrolled and screened, and the number of subjects needed to complete the research procedures.

For Aim 2, statistical power is analyzed based upon assumptions that we have N=50 total or N=25/group complete all 3 data collection time points with complete observations. We will over sample participants at baseline to offset the predicted dropout rate and ensure the proposed sample size in the final visit.

13.0 Recruitment Methods

- 13.1 Describe when, where, and how potential subjects will be recruited.
- 13.2 Describe the source of subjects.
- 13.3 Describe the methods that will be used to identify potential subjects.
- 13.4 Describe materials that will be used to recruit subjects.
- 13.5 Describe the amount and timing of any payments to subjects.

Recruitment will take place in Aim 1 and Aim 2 of this study. For Aim 1, an expert panel will be selected to rate the accuracy, relevance, and feasibility of the intervention. Purposeful recruitment methods will be used. For example, flyers will be placed in strategic locations. Referrals and recommendations will be accepted. The expert panel will include four midlife Black women laypersons, three researchers (identified as experts by having a doctoral degree and strong record of publication), and three integrative health care specialists. \$100 is allocated for each reviewer for their time and effort (total \$1000).

Aim 2 will include CBPR techniques, such as community engagement, to assist in recruiting midlife Black women in the Greater Cincinnati area. Collaboration with an experienced community research advisory board will guide the recruitment efforts and selection of study sites. Recruitment will involve use of fliers, referral, snowballing, and purposeful sampling in targeted communities. Fliers may be posted in businesses, on list serves, or group websites to increase distribution. All potential participants will be provided with written information about the nature, purpose, and possible risks and benefits of the study. Study participants will receive a \$20 incentive per person at each data collection time point: baseline (before the start of the program), 8 weeks (at completion of the study), and 12 weeks. For 50 participants with three data collection time points, the total is \$3000.

14.0 Withdrawal of Subjects*

14.1 Describe anticipated circumstances under which subjects will be withdrawn from the research without their consent.

Participants may be withdrawn from the research without consent if they exhibit behaviors that disrupt the study activities, fail to adhere to online confidentiality guidelines, or are disrespectful and/or distressing to other participants in the study.

14.2 Describe any procedures for orderly termination.

The decision for termination will be made by the PI. Any and all communications regarding a termination and related procedures will be initiated by the PI. Only relevant research personnel will be advised and appropriate documentation will be placed in RedCap.

14.3 Describe procedures that will be followed when subjects withdraw from the research, including partial withdrawal from procedures with continued data collection.

When participants choose to withdraw from the research, all data collection and contact will cease. Upon withdrawal, the participant will be required to return the B-SWELL study tablet and materials. Documentation will be updated in RedCap to reflect the change. Only relevant research personnel will be Advised of the participant's status.

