Interventions and Treatment Fidelity Methods: The B-SWELL intervention will follow procedures such as those proposed in Figure 1 and will be refined prior to trial based on feedback from the community collaborators and expert ratings (Aim1). Participants will be randomized to either the B-SWELL or WE groups. Both groups will be introduced to the LS7 materials. The B-SWELL will receive additional instruction about stress. B-SWELL and WE group sessions will occur on different dates and times and, participants will be asked not to share experiences with women outside of their assigned group. Participants will also be asked to secure private location when attending the virtual sessions to ensure privacy and confidentiality. Treatment fidelity of both groups will be monitored using Borrelli's Treatment Fidelity Checklist (Design, Training, Delivery, Receipt, Enactment). Facilitators of the intervention and control groups will be trained prior to the start of the trials.. Zoom meetings will be audio taped for quality assurance.

Data Collection Procedures: Aim 2. Data collection will occur at baseline, 8 weeks, and 12 weeks. Baseline data will be collected from B-SWELL and WE participants using telephone interviews conducted by trained, blinded research assistants. Data collection at 8 and 12 weeks may be collected via phone interview or through a REDCap link on the B-SWELL study tablets provided to B-SWELL and WE participant. Completion of the surveys (interview or via REDCap link) is expected to last 30-45 minutes for each timepoint. Instruments are listed in Table 5. 3.4.d.

Randomization Procedures: Following baseline data collection, participants will be randomized to either the B-SWELL or WE group using 1:1 block randomization to promote equal group sizes. The randomization allocation sequence will be blinded to data collectors to avoid bias during follow-up data collection telephone interviews. Following randomization, the PI or research assistant will notify the participant of their group assignment and upcoming group meetings. Treatment fidelity will be monitored using the Borrelli's Treatment Fidelity Checklist (Design, Training, Delivery, Receipt, Enactment).

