Protections against risk. Participants may choose not to answer items during interviews or participate in portions of the intervention program with which they are uncomfortable. In the unlikely event that a participant appears to be distressed, she will be referred to appropriate resources or be given the telephone number for the national Suicide [contact]; [name]) if appropriate. The PI will inform the IRB of any adverse events and/or any amendments to the protocol. Training for data collectors also will include how to respond to any potential adverse events experienced by participants, such as suicidal tendencies or severe depression. Participants with these types of problems will be given information about how to seek help and will be encouraged to inquire whether medication and/or psychological counseling would be helpful. In the event of suicidal thoughts, the PI or research staff may contact a health care provider on the participant's behalf so that they can contact the participant directly to determine if treatment is necessary.

To avoid loss of confidentiality during the online Zoom sessions, participants will be asked to find a private location from which to attend the online Zoom sessions. Additionally, participants will be required to attend Zoom sessions with video and will be asked to keep session discussions and activities private.

Only authorized study personnel will have access during the Zoom sessions, Zoom audiotapes or transcriptions, REDCap data, database, or contact information for study participants and expert panel members. For data analysis, study ID numbers will be generated to protect the identity of the participants in the final data set. Participants will not be identified in any way in reports or manuscripts from the study. Data from surveys will input directly into a REDCap database either manually or via the link on the study tablets. REDCap is backed up nightly by the university. Only authorized study personnel will have access to REDCap. Any calls to participants will be made to a telephone number provided by the participant at a time that is convenient for the

participant. Research staff will make calls from a private location in order to protect confidentiality. Informed consent forms and contact information from participants will be stored separately in a locked file cabinet to protect confidentiality.

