17.0 Data Management* and Confidentiality

17.1 Describe the data analysis plan, including any statistical procedures or power analysis.

In Aim 1 and Aim 2a, numerical measures will be summarized using descriptive statistics (i.e., means, standard deviations, and frequencies) regarding expert ratings of degrees of accuracy, relevance and feasibility of new components of the B-SWELL program (Aim 1), and recruitment, retention, treatment fidelity ratings, and satisfaction ratings (Aim 2a). For Aims 2b and 2c, numerical dependent variables (stress, self-efficacy, LS7 scores, unhealthy days, perceived general health, depressive symptoms) will be inspected of empirical distributions to ensure they meet conditions for parametric statistical models. Variable transformation will be used otherwise. All statistical tests will be performed using SPSS Version 25. Parameter estimates with P-values less than .05 will be considered statistically significant. Assumptions related to each statistical test used will be checked using residual plots, qq-plots, and tests for homogeneity of variance/ covariance. In Aim 2b, continuous mediators (stress, self-efficacy) will be compared between groups (B-SWELL vs WE) using t-tests at each visit (baseline, 8 weeks, 12 weeks).

In Aim 2c, using mixed effect models, primary (i.e., LS7 summary scores) and secondary outcome measures (i.e., unhealthy days, perceived general health, depressive symptoms) will be assessed for their associations with time (baseline, 8 weeks, 12 weeks), group (B-SWELL vs. WE), and interaction. In particular, each of the outcome measures will be treated as the dependent variable, and the time effect, group effect, and the interaction will be treated as independent variables or fixed effects of interest in the mixed effect model. Random effects will be used to account for within person correlation due to repeated measurements. Other covariates, such as demographics and attendance rate, will be controlled for by including them in the model and checking for their interaction with the intervention. Post hoc analysis of group means will be compared cross-sectionally, as well as longitudinally between time points (such as week 8 or 12 vs. baseline). Considering the limited sample size for this pilot-type of study, statistical tests will not be adjusted for multiple comparisons in post hoc analyses. Significant findings will be considered preliminary in nature and inspire future research.

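### Section 14 treats leaving the study as one event: it gives no route to leave the sessions and stay in follow-up, and does not say whether outcomes are sought from women the PI removes

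*Combined protocol and SAP*

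**What the plan says.** - **Voluntary withdrawal (section 14.3).** The prompt asks for procedures "including partial withdrawal from procedures with continued data collection". The answer is: "When participants choose to withdraw from the research, all data collection and contact will cease". It continues: "Upon withdrawal, the participant will be required to return the B-SWELL study tablet and materials". No partial route is described.
- **Removal by the PI (sections 14.1 and 14.2).** "Participants may be withdrawn from the research without consent if they exhibit behaviors that disrupt the study activities". Breaches of online confidentiality and conduct that is disrespectful or distressing to others are further grounds. The PI decides. Neither section mentions later data collection.
- **Partial participation (section 6.3, repeated in 19.1).** "Participants may choose not to answer items during interviews or participate in portions of the intervention program with which they are uncomfortable".
- **Follow-up (section 6.2.2).** "Data collection will occur at baseline, 8 weeks, and 12 weeks". The 8- and 12-week surveys may be done by telephone interview or through a link on the study tablet.
- **Analysis (section 17.1).** Aim 2b uses t-tests at each visit. Aim 2c uses mixed models, and "Other covariates, such as demographics and attendance rate, will be controlled for by including them in the model". Multiple imputation is optional. No analysis population is stated.
- **Dropout (section 12.2, repeated in 17.1 and 25.1).** The plan will over-sample at baseline to "ensure the proposed sample size in the final visit". No dropout rate is given.

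**The concern.** A woman who tells staff that she wants to leave the group has one documented exit, and it ends her follow-up. She might be willing to answer a telephone survey, but the plan has no step that asks her, and the stop on contact prevents asking later. A woman removed for her conduct in sessions is withdrawn from the research as a whole, not just from the sessions.

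Both events happen after randomisation and can depend on what goes on in the sessions, which differ by arm: B-SWELL adds content on stress. If the women who go differ from those who stay, and this pattern differs between arms, the comparison at 8 and 12 weeks is no longer between the groups as randomised.

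Aim 2a is also affected. Retention is a named feasibility outcome, and the findings are meant to support a larger trial. That trial needs to know how many women leave the programme and, separately, how many will not give outcome data. For a woman who withdraws under section 14.3, the two become one event.

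**Working it through.** **Step 1: who is covered.** Setting the texts side by side:

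| Situation | What the text implies for 8- and 12-week outcomes |
|---|---|
| Skips sessions or parts of the programme | Still due; sections 6.3 and 19.1 allow it, and attendance is a model covariate |
| Chooses to withdraw from the research | Not collected (14.3) |
| Wants to leave the sessions only | No route described, although 14.3 asks for one |
| Withdrawn by the PI | Not stated; the words used are withdrawal from the research |

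**Step 2: is removal judged blind?** Section 6.2.2 blinds the data collectors. It also has the PI or a research assistant tell each woman her group, and section 25 has the PI review session audiotapes. The person who decides on removal therefore knows the arm.

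**Step 3: what the analyses do.**
- Aim 2b t-tests use women with a value at that visit. A withdrawn woman is omitted unless imputed.
- The Aim 2c mixed model keeps visits before withdrawal. A woman who leaves before week 8 contributes her baseline only, so her later outcome is inferred from women who stayed.

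**Step 4: the plan's own power figure.** Inputs from section 17.1: 25 complete per arm, standardised effect 0.87, two-sided 0.05. Noncentral-t power is 85.4%, against 85% stated. The figure reproduces and is not in dispute.

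**Step 5: size of a possible bias.** Let m be the share of an arm that is lost and g the gap, in SD, between that arm's completers and its lost women. The whole-arm mean is (1 − m) × C + m × (C − g) = C − m × g, where C is the completer mean. So the completer mean is off by m × g. The bias in the difference is (m × g in B-SWELL) − (m × g in WE).

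The documents give neither m nor g. Under assumed values, the shift in one arm (SD) is:

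| m | g = 0.25 | g = 0.5 | g = 1.0 |
|---|---|---|---|
| 10% | 0.025 | 0.05 | 0.10 |
| 20% | 0.05 | 0.10 | 0.20 |
| 30% | 0.075 | 0.15 | 0.30 |

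Equal losses with equal gaps cancel between arms.

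**Step 6: does over-sampling help?** For 50 completers at an assumed 20% loss, enrolment is 50 / (1 − 0.20) = 62.5, so 63. The count is restored, but m is still 20%, so m × g does not change.

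**The case against.** The strongest reply is that ceasing contact when someone withdraws from research is correct, and that the rest is a wording gap in a minimal-risk pilot whose stated emphasis is on trends. The first half stands: a woman who declines further data collection must be left alone. The second half stands in part. The consequence is modest, but the rule is operative as written, and the section's own prompt asks for the missing route.

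A reader might infer more than the documents support:

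- *That any woman who stops attending is lost.* No text treats missed sessions as withdrawal, and the provisions on skipping parts of the programme and on attendance as a covariate point the other way.
- *That outcome collection stops by rule for women the PI removes.* The cessation sentence covers women who choose to withdraw. Extending it to removed women is a reasonable inference from the wording of 14.1, but it is not stated. Nor do the documents suggest that removal would be frequent or would differ by arm.
- *That withdrawn women drop out of every comparison.* Aim 2c keeps their earlier data, and imputation is permitted.
- *That power falls below the stated level.* The plan commits to over-sampling so that 25 per group complete, so a power loss does not follow.
- *That the bias favours B-SWELL.* Nothing in the documents gives its direction.

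It can also be said that attendance is recorded separately, so session and survey dropout can already be told apart. That is true for women who stay in the research. For those who withdraw, both end together, and retention is not defined.

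**Conclusion.** The point holds in a limited form. Section 14 does not separate stopping or being removed from sessions from withdrawing from data collection. As a result, it gives up outcomes that some women might have been willing to provide, and for women the PI removes it leaves open whether outcomes are sought. Over-sampling, the mixed model and optional imputation do not recover the unobserved values.

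The bias cannot be sized from the documents. It depends on the share lost, how those women differ from completers, and whether this differs by arm. With 20% lost from one arm and a 0.5 SD gap, both assumed, that arm's completer mean shifts by 0.10 SD. This is small beside the 0.87 SD effect in the power statement. It describes completer means as used in the Aim 2b t-tests; the mixed model may reduce the shift as far as earlier data predict the missing values. The case for changing the plan rests as much on a clear retention result for Aim 2a as on bias. The change should be made, but the plan does not fail without it.

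**What to change.** - In 14.1 and 14.3, distinguish stopping or being removed from sessions from withdrawing consent for data collection. The grounds on which the PI may remove a woman need not change.
- Ask each woman who stops or is removed from sessions whether she will still complete the remaining 8- and 12-week surveys. Use telephone interviews by the blinded data collectors, so that return of the tablet does not matter. Cease contact only if she declines.
- In 17.1, state that the data obtained are analysed in the assigned arm.
- Under Aim 2a, report session dropout and survey dropout separately by arm.

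Cost: a few sentences in the protocol, one line in the information sheet and some extra calls. Survey payments stay within the per-participant amount in section 13: 3 × $20 = $60 each, and 50 × $60 = $3000 in total. That total covers 50 women, so any over-sampled women would be an additional cost with or without this change.

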15.0 Risks to Subjects*

15.1 List the reasonably foreseeable risks, discomforts, hazards, or inconveniences to the subjects related the subjects' participation in the research.

There is minimal risk in this study. Some items asked during the data collection phone calls or group (intervention or attention control) sessions may focus on negative emotions or experiences. There is also a risk of loss of confidentiality for participants and expert raters involved in the study due to the online Zoom platform used for group sessions. To avoid loss of confidentiality during the online Zoom sessions, participants will be asked to find a private location from which to attend the online Zoom sessions. Additionally, participants will be required to attend Zoom sessions with video and will be asked to keep session discussions and activities private

There are no anticipated physical, social, legal, or other anticipated risks connected with the proposed procedures. There are no investigational drugs or devices associated with the study, and we do not anticipate any serious adverse events. Adverse events attributed to data collection or participation in the group (intervention or attention control) sessions are unlikely. Data collection will take place via phone for each of the third data collection time points (baseline, 8, and 12 weeks). The time estimated for data collection is 24 to 34 minutes. Data collection when be scheduled at the convenience of the participant.

15.2 If applicable, indicate which procedures may have risks to the subjects that are currently unforeseeable.

N/A

15.3 If applicable, indicate which procedures may have risks to an embryo or fetus should the subject be or become pregnant.

N/A

15.4 If applicable, describe risks to others who are not subjects.

N/A

16.0 Potential Benefits to Subjects*

16.1 Describe the potential benefits that individual subjects may experience from taking part in the research.

Participants involved in the study may perceive benefit by knowing that they are assisting in the development of a novel intervention program tailored to midlife Black women and designed to decrease stress and CVD risk. Participants in this study will have improved knowledge about stress, stress reducing strategies, personal cardiovascular disease risk, and healthy lifestyle behaviors. Participants may also increase their social and support networks and awareness of resources within their communities. In addition, participants who engage in the program may improve their health through the adoption of healthy lifestyle behaviors and decrease their overall CVD risk.

16.2 Indicate if there is no direct benefit. Do not include benefits to society or others.

N/A

17.0 Data Management* and Confidentiality

17.1 Describe the data analysis plan, including any statistical procedures or power analysis.

In Aim 1 and Aim 2a, numerical measures will be summarized using descriptive statistics (i.e., means, standard deviations, and frequencies) regarding expert ratings of degrees of accuracy, relevance and feasibility of new components of the B-SWELL program (Aim 1), and recruitment, retention, treatment fidelity ratings, and satisfaction ratings (Aim 2a). For Aims 2b and 2c, numerical dependent variables (stress, self-efficacy, LS7 scores, unhealthy days, perceived general health, depressive symptoms) will be inspected of empirical distributions to ensure they meet conditions for parametric statistical models. Variable transformation will be used otherwise. All statistical tests will be performed using SPSS Version 25. Parameter estimates with P-values less than .05 will be considered statistically significant. Assumptions related to each statistical test used will be checked using residual plots, qq-plots, and tests for homogeneity of variance/ covariance. In Aim 2b, continuous mediators (stress, self-efficacy) will be compared between groups (B-SWELL vs WE) using t-tests at each visit (baseline, 8 weeks, 12 weeks).

In Aim 2c, using mixed effect models, primary (i.e., LS7 summary scores) and secondary outcome measures (i.e., unhealthy days, perceived general health, depressive symptoms) will be assessed for their associations with time (baseline, 8 weeks, 12 weeks), group (B-SWELL vs. WE), and interaction. In particular, each of the outcome measures will be treated as the dependent variable, and the time effect, group effect, and the interaction will be treated as independent variables or fixed effects of interest in the mixed effect model. Random effects will be used to account for within person correlation due to repeated measurements. Other covariates, such as demographics and attendance rate, will be controlled for by including them in the model and checking for their interaction with the intervention. Post hoc analysis of group means will be compared cross-sectionally, as well as longitudinally between time points (such as week 8 or 12 vs. baseline). Considering the limited sample size for this pilot-type of study, statistical tests will not be adjusted for multiple comparisons in post hoc analyses. Significant findings will be considered preliminary in nature and inspire future research.

Power. Statistical power is analyzed based upon assumptions that we have N=50 total or N=25/group complete all four data collection time points with complete observations. Should there be any concern of dropout from the study, we will over sample participants at baseline to offset the predicted dropout rate and ensure the proposed sample size in the final visit. The statistical tests are two sided with a targeted significance level of 0.05. In Aim2b and Aim2c post hoc analyses when we compare means using a two group t-test with equal variances assumption, we will reach 85% power to detect an effect size (i.e. difference of means/standard deviation of the difference) of 0.87.73 In Aim2c when we compare means using a paired t-test between visits in a group, we will reach the 85% power to detect an effect size of 0.63.73 If possible, and plausible, missing data could be included into analysis after multiple imputation, thus increasing the sample size and statistical power to detect differences. The main emphasis will be on exploring data trends to inform future work, rather than

significance, since this is a feasibility study. Significance will be emphasized when testing efficacy of the B-SWELL intervention compared to the WE attention control group in a future, well-powered RCT.

17.2 Describe the steps that will be taken to secure the data during storage, use, and transmission.

All study data and tracking will be entered into an electronic data system, REDCap (www.REDCap.org), a secure research electronic data management system with validated data entry, audit trails for tracking data manipulation, and export procedures. It is HIPAA complaint satisfying all local, state, and federal regulation for the capture and storage of private health information for research purposes. The PI is familiar with RedCap through prior research projects. The PI is committed to compliance with HIPAA, data safety procedures, NIH recommendations, and CITI trainings. All research personnel will be trained in the use of secure data and RedCap prior to their participation in the study and any communication with participants.

The Zoom platform has been approved by the UC Department of Research. Zoom provides advanced security and infrastructure to provide security during online activities. Administrators have the ability to perform secure log-ins, start a secured meetings with password, and schedule secured meetings with password. Secure meeting capabilities include the following:

- Role-based user security (i.e. waiting room, lock a meeting, end a meeting, expel a participant)
- Host and client authenticated meeting
- Open or password protected meeting
- Edit or delete meeting
- Host controlled joining meeting
- In-meeting security (i.e. all data is encoded)
- Authentication

The account administrator (study PI) will have the following security capabilities:

- Secure login options using standard username and password or SAML SSO
- Add user and admin to account
- Delete user from account Security Guide Zoom Video Communications, Inc. July 2020
- Manage account dashboard and cloud recordings
- 17.3 Describe any procedures that will be used for quality control of collected data.

For Aim 1, ratings will be obtained using survey tools adapted from a validated satisfaction questionnaire. For Aim 2, data will be collected using validated survey tools. In addition, data will be collected via phone to decrease the risk for missing data. Data collected via the B-SWELL study tablet will be linked directly to the REDCap. REDCap will be used to organize, store, and secure data. Only trained research personnel will handle the data and have access to REDCap.

17.4 Describe how data or specimens will be handled study-wide:

Rating surveys, self-report survey data, and satisfaction ratings will be gathered from the expert panel and participants (Aims 1 & 2) and entered directly into a REDCap database via laptop computer or REDCap survey link (for experts). Intake data will be labeled with study ID numbers and stored separately. Names, contact information, or any other identifiers will be stored separately from all data that is collected. Access to the

database, contact information, or linkages between study ID numbers and participants enrolled in the study will be limited to the investigators. Participants will not be identified in reports or manuscripts from the study. All paper forms and study materials will be stored in locked file cabinets accessible only to authorized study personnel. All computers, servers, and electronic files used in the study will be password protected and accessible only to authorized study personnel. Authorized study personnel will include the investigators and research staff involved in the study.

Data will be handled by trained research personnel only. Trained research personnel will be responsible for collecting and logging data. Data will be stored for the duration of the study and for five years following the completion of the study.

